6.2 Study participant support: Participants will have support from all members of the

Summary of Consent Procedures

Consent for the Care Responders Response

When a 111/999 call is made, service users give **verbal consent** for an emergency response vehicle to attend. At the scene, police officers go in first to check safety we before a mental health practitioner (MHP) enters. The Care Responders pilot will follow this same process, supporting young people in crisis with a specialist CAMHS clinician.

Assent and Consent Process for All

At the scene of a crisis, the attending MHP will ask if the parent/carer (and young person aged 16–18 if appropriate) would like to be contacted about the study. If the situation is too distressing, no consent will be taken, but information will be left for the family.

There are **multiple options** for families to give informed consent or assent later:

- Sign a form in person
- Return a form by post 📫
- ✓ Email a signed form
- Give recorded verbal consent
- ✓ Provide assent and consent via the consent form on Qualtrics ■ ■

Consent will always be checked before any data is collected, and again at 6-month follow-up, where appropriate, to make sure everyone's still happy to take part.

Other Participation Options

- 1. Families who have engaged with emergency or crisis services for a young person's mental health crisis in the past 2 years can choose to join reflective interviews the online Qualtrics survey
- 2. The nested case study with Mersey Care will also invite 20 young people, 20 parents/carers, and 20 practitioners to share their experiences through the same participation options.

research team, including AT (PPIE lead), the peer research assistant, and the Head of Patient and Carer Experience and Engagement at Pennine Care. If a participant is considering leaving the study earlier than planned, all efforts will be made to explore a support plan for their engagement, collaboratively with the participant. All young people will have access to the Pennine CAMHS Mental health helpline and supportive resources for families and young people

(https://www.penninecare.nhs.uk/camhs/urgent-help). A similar approach will be taken for stakeholders involved in the study. Relevant helplines (e.g., Mind, Samaritans, Papyrus) will also be offered as points of support external to the Trust and research team. The Trust has a range of support services available for employees, which will be shared with colleagues at relevant points throughout the study.

6.3 Payments, rewards, and recognition: We have followed the INVOLVE guidance on renumeration for stakeholders and participants, outlined in the detailed budget and cost justification.

6.4. Taking Informed Consent

Consent for the intervention from service users.

Based on the existing NHS Standard Operating Procedure (SOP), service users provide verbal consent for an emergency response vehicle to attend during their 111/999 call. The current practice for a MHJRC joint response is that "Police Officers will enter the scene first and assess the situation prior to the mental health practitioner entering the address or interacting with the individual(s). Only when the officer deems it safe to do so will the practitioner exit the police vehicle and enter the address/location or join the responder from GMP from within the wider location if already on site (e.g., custody suite). It is appreciated that situations can however be very dynamic, and officers will respond accordingly, having due regard for the safety of the practitioner. It should be remembered that the practitioner will not be wearing a protective vest because they are not attending in the role of an emergency first responder, but of a mental health practitioner." (SOP, 2022, p.7). As the only change for our study is that the responders are attending a younger population with the specialist expertise of a CAMHS Band 7/8 practitioner, most likely a clinical psychologist, we will follow the same process as outlined in the original SOP. Once in attendance, the Police Officer and MHP will follow standard processes for risk assessment and clinical decision making, drawing upon evidence-based practices to diffuse tension and risk, providing a compassionate space to hear from the young person in crisis and other people on scene, and discuss next steps with the young person and any responsible adults present.

Consent for the evaluation from prospective participants

As per the existing SOP, "Service user's verbal consent to engage with the evaluation will be gathered on scene by the attending MHP and will be captured within clinical documentation. Following MHJRC callout, where a service user has consented to engage with the evaluation process, they will be contacted by a member of the research team and, where confirmed to be consenting once more, will engage in the evaluation." (SOP, 2022, p.15). We will follow this process for data collection at T1 (within 12 weeks of the first contact with emergency services). We will only gain consent to contact from parents/caregivers, not young people at the point of the response. Due to the distress young people and parents/carers may experience

during mental health call outs, we propose two options for gaining informed consent for research participation in the evaluation for young people who access the Care Responders pilot.

Potential participants who hear about the study and wish to hear more will be able to contact the research team via email or phone. Once in touch, the research team will follow the assent/consent process outlined below.

Overall, informed assent and/or consent will be obtained prior to any data collection. Before the first point of data collection, participants will be provided with multiple options to confirm and document their informed consent, depending on whether contact with the research team will be face-to-face or via remote means. These will include: 1) signing a hard copy of the consent form during face-to-face meetings with research workers; 2) returning a signed hard copy of the consent form to the research team via standard mail (using a pre-paid return envelope provided by the research team); 3) returning a signed electronic copy of the consent form to the research team via email; or 4) providing audio-recorded consent (this will be recorded by research workers using an encrypted recording device and stored separately from any research data collected from study participants). The research worker will sign the consent form on behalf of the participant as instructed to do so during the consent taking process of the call. The research worker will note the consent process briefly on the consent form, alongside the date and time consent was taken.

Due to the distress young people and parents/carers may experience during mental health call outs, we propose four options for gaining informed assent/consent for research participation in the evaluation.

Care Responders Option 1: Young people aged under 16 years old who receive support from the Care Responders pilot will not be asked by the attending team if they consent to being involved in the study as a research participant. If the attending mental health practitioner considers a young person aged 16-18 years old and/or the parent/caregiver able to read and understand the consent to contact request form, ask questions, and consent to being contacted in future, they will be able to do so. This decision will depend on the mental health and wellbeing assessment undertaken as part of the response. If the young person aged 16-18 years old and/or the parent/caregiver is considered too distressed to consent to being contacted, the attending practitioners will only leave information about the study with the family for them to consider in their own time. Information about participation through pathways one and five will be provided.

Care Responders Option 2: If it is considered the potential participants (young people of all ages and parents/caregivers) are too distressed to discuss consent to contact for the research study, contact information will be stored securely by the

attending Care Responders practitioners according to data storage procedures for the study. A follow up phone call will be made a few days later to see if the parent/caregiver (if the young person is aged under 16 years old) and or parent/caregiver or young person (aged 16-18) would like to discuss research participation in the evaluation. Additionally, an information flyer about the study will be left in the family's home when the Care Responders practitioners leave, or given to the parent/caregiver in the attending location if not at home. The young person and/or parent/carer can then contact the research team and opt-in if they would like to later in the recruitment window (within 12 weeks of contact). Information about participation through pathways one and five will be provided.

TAU Option 1: For potential participants who access TAU, the responders who attend to them will provide a consent to contact form. If the parent/carer would like to hear more about the study, they can complete the consent to contact form, return it to the responder, who will store it securely at their base (e.g., police station, NHS premises) and notify the Care Responders team to collect it. Hard copies will therefore be collected by a member of our research team within two weeks of notification. Additionally, once consent to contact has been established, the administrator at the responder's base will send a digital copy of the form to the research team, so the young person and/or parent/carer can be contacted quickly. Digital copies will be stored securely by the research team and paper copies and digital copies will then be destroyed by the base team. Again, if it is not appropriate to follow this process (e.g., a young person needs to be referred immediately for emergency hospital care), the responsible adult will be given a contact and information leaflet. The young person and/or parent/carer can then contact the research team and opt-in if they would like to later in the recruitment window (within 12 weeks of contact). Information about participation through pathways three and five will be provided.

TAU Option 2: Due to the dynamic nature of emergency care and relatively ambitious recruitment target we have for TAU; we will offer an opportunity for potential participants who hear about the study and wish to take part to opt-in to reflective interviews about their past experiences. This participation will need to operate differently to offer more flexibility. For these participants, they will need to have engaged in a youth emergency response for mental health crisis within the last two years, as a young person or parent/carer. These participants will hear about the study through the aforementioned routes, contact the research team, declare their interest to participate, and provide basic information so a member of the research team can assess eligibility. Once eligibility is confirmed (via email, phone or Teams), a member of the research team will arrange to send an information sheet and arrange an in person or digital appointment to discuss and take consent. Once assent/consent has been taken, the participant will take part in a reflective qualitative interview about their experience at a convenient time and place for the participant or the participant will be able to take part through the Qualtrics survey.

Nested Case Study: Young people (N=20), parents/carers (N=20) and practitioners (N=20) will opt-in to take part in reflective qualitative discussions about their experiences of child and adolescent crisis care in Merseyside. Once eligibility is confirmed (via email, phone or Teams), a member of the research team will arrange to send an information sheet and arrange an in person or digital appointment to discuss and take consent. Once assent/consent has been taken, the participant will take part in a reflective qualitative interview about their experience at a convenient time and place for the participant.

At any subsequent time points of data collection, the research worker will ask if the participant still provides their assent/consent and will mark the participant's confirmation of assent/consent on the CRF. If the participant wishes for more information, the research worker will go through the original documentation. Data collection will only go ahead following the giving of informed assent/consent.

Concluding details on assent/consent

Following enrolment and assent/consent, participants will be asked to complete a questionnaire assessing relevant demographic information (Laurens et al., 2020) (e.g., age, gender, ethnicity, family circumstances) and brief clinical history information (history of past service use, any comorbid diagnoses etc.).

For participants engaging with the Care Responders intervention evaluation:

Following gaining consent/assent, baseline (T1) data will be collected from all participants. At all research assessments, young people will be asked whether they prefer to speak to the researcher alone or in the presence of their parent/carer, or another trusted adult. Parents/carers will also be asked if they would like to speak with the researcher privately, or with their child present. The same process will be followed at 6-month (T2) follow-up, to ensure the assent/consent giving process is based upon ongoing review, consideration, and freedom of choice.

Engagement process for participants

At the beginning of research engagement, the research study will be explained to potential participants in person, via Teams, email, or by telephone, depending upon the patient's preference. Consent (participants aged 16-years-old and over) and assent (participants aged 15-years-old and under, with parental/caregiver consent also required) to participate will be obtained during an initial meeting if the patient would like to take part or via Qualtrics if the participant has opted to take part through the online survey option.

Following enrolment, participants will be asked to complete a questionnaire assessing relevant demographic information (Laurens et al., 2020) (e.g., age, gender, ethnicity, family circumstances) and brief clinical history information (history of past service use, any comorbid diagnoses etc.).

Following gaining consent/assent, baseline (T1) data will be collected from all participants. At this point, it will be noted on the participant tracker how many weeks have passed since the crisis for which the young person sought help. This will help us review the data in the context of the number of weeks that have passed (maximum 12 weeks for pathways one and three) since the crisis. At all research assessments, young people will be asked whether they prefer to speak to the researcher alone or in the presence of their parent/carer, or another trusted adult. Parents/carers will also be asked if they would like to speak with the researcher privately, or with their child present. The same process will be followed at 6-month (T2) follow-up, to ensure the assent/consent giving process is based upon ongoing review, consideration, and freedom of choice.

6.3.1 Additional consent provisions for collection and use of participant data

The consent form used for the study will include optional items of consent related to additional collection and use of participant data. It will be made clear that these additional consent options are non-mandatory and that declining additional consent will not prevent them from taking part in the trial.

Based on prior experience of working in this field and anticipated media interest in this study, we will also ask participants to separately consider providing consent to be passed information about prospective media opportunities (e.g., radio or TV interviews). This approach will mean that consent for the research study is clearly separate from consent to be contacted about media opportunities, although participants who wish to be contacted will have the choice. In previous studies conducted by the research team, participants were often keen to talk about their experiences within media features, which is why we include this element in the protocol, to offer participants the option.

All participants will also be asked whether they give permission for: 1) some of the assessment to be audio recorded for quality checking and for improving study procedures and assessments; 2) the recordings to be used for supervision/teaching/training; 3) their anonymised data to be used for secondary analysis research; 4) their anonymised data to be made available for data-sharing with other research teams; 5) being contacted at a later stage for participating in further studies related to this area of research; 6) being contacted at a later stage to receive a summary of the study findings; and 7) having their participation in the study recorded in their clinical notes.

6.3.2 Withdrawal of consent and withdrawal criteria

Participants will be free to withdraw from the study at any time. If a participant is deemed to lose the capacity to assent/consent to research while taking part in the study, the participant will be withdrawn from the study. A participant may be withdrawn if the research team are notified of a significant potential threat to the safety of a member of the research team or if a participant displays aggressive or abusive behaviour towards a member of the team. These decisions would be made in consultation with appropriate clinical colleagues and would occur on a case-by-case basis.

6.4 Data Collection

At T1 and T2, participants will be asked to complete a battery of measures and take part in semi-structured interviews about their experiences and, later, reflections upon those experiences.

Methodologically, exploring the MHJRC through a realist evaluation (workstream 2) will offer a nuanced view of how the MHJRC works as an intervention for the communities it serves. We will expand and refine our programme theory from workstream one (realist synthesis) and consider the differences between current practices and the MHJRC by exploring how existing approaches relate to people's lived experiences of the MHJRC through the collection of qualitative and quantitative data. Our realist programme theory will be tested (confirmed, refuted, or refined) through a realist evaluation using mixed methods data.

Data collection from young people and, where possible, their parents/carers, will be tailored based on the findings of workstream one. However, for the purposes of ethical review, we can confirm data collection will include:

- 1. Contextual features, identified in Workstream 1, that influence service user experiences.
- 2. Demographic characteristics, feedback on relationships, and individual satisfaction ratings.
- 3. Exploring relationships between quantitative measures of outcomes and contextual factors.
- 4. In-depth qualitative exploration of processes underpinning the deeper causal relationships between the variables from the quantitative survey, which will ensure that demi-regularities between variables across the sample are not in themselves assumed to be causal. Exact interview questions will be finalised based on workstream one, although an indicative topic guide formulated through our initial literature review and stakeholder discussions is provided for ethical review.

Quantitative surveys of service user experiences of the MHJRC (N=100, recruited through the MHJRC) and people who have engaged with traditional services to a 111/999 call (N=100, recruited through the MHUT) will be collected at the start (T1, within 12 weeks of the first contact with emergency services (i.e., traditional response to a 999 call or the MHJRC) and 6-month (T2) follow-up.

6.4.1. Measures

The Strengths and Difficulties Questionnaire (SDQ; routinely employed screening and outcome measure in CAMHS) will be used at T1 and T2. The SDQ is a brief behavioural screening questionnaire for 2-17-year-olds. This single-informant measure assesses child-wellbeing and is used by clinicians at the point of referral and exit in CAMHS. Our choice of other questionnaires will be finalised by the programme theory but will likely include:

T1

Analysis of routine data sets held by GMP and PCFT (e.g. care plans, A&E admissions, acute care pathway referrals) in relation to each contact who has engagement with the MHJRC, with an additional EDI lens to evaluate whether the routine data points capture information about the context of the individual that could inform greater cultural sensitivity and accessibility. Experience of Service Questionnaire (ESQ) Child Self-report for 9–11-year-olds, ESQ Child Self-report for 12-18-year-olds, ESQ Parent/carer report

Therapeutic Experience Scale with young people, parents/carers, and staff (STAR-P and STAR-C)

KidCOPE scale 7-12, KidCOPE scale 13-18

Child and Youth Resilience Measure-Revised (CYRM, 5-9-years-old; CYRM, 10-23years-old)

Parental Stress Scale (PSS)

Session Rating Scale (SRS)

Short Mood and Feelings Questionnaire (sMFQ)

EQ-5D-Y-3L child-friendly EQ-5D version (EQ-5D-Y)

MHJRC PCFT staff will keep tabulated records of how time is spent. The study team will collaborate with members of the adult MHJRC team to develop a 'heat map' of youth and adult need/call outs across the service footprint, considering location, frequency, and key timings.

T2

Repeat ESQ, KidCOPE, CYRM-R, PSS.

These measures will address the research questions by gathering data on the impact of the MHJRC on wellbeing, service experience, therapeutic nature of relationships,

coping ability over time, and stress. This data will be enriched through the collection and analysis of qualitative data from the interviews.

!			
 			
1			

Time point / Participant group	In person/video call T1 (within 12 weeks of engagement with MHJRC/TAU)	In person/ video call T2 (3-month follow-up)	In person/ video call T2 (6- month follow-up)	Qualtrics Survey T1 Route 1: within 12 weeks of engagement with MHJRC/TAU Route 2: Within two years	Qualtrics Survey T2 (Only if Route 1: T1 was within 12 weeks of engagement with MHJRC/TAU)
Children/young people	Personal context Nature of crisis Demographics SDQ – CYP ESQ SRS sMFQ CYRM-R KidCOPE Interview EQ-5D-Y	ESQ KidCOPE CYRM-R EQ-5D-Y-3L Interview	ESQ KidCOPE CYRM-R sMFQ Interview/Workshop	Personal context Nature of crisis Demographics SDQ – CYP ESQ SRS sMFQ CYRM-R KidCOPE Interview questions EQ-5D-Y	Personal context Nature of crisis Demographics SDQ – CYP SMFQ CYRM-R KidCOPE Interview questions
Parent/Carer	Interview SDQ – Parent version PSS STAR-P SRS EQ-5D	ESQ PSS STAR-P EQ-5D Interview	ESQ SDQ and PSS STAR-P EQ-5D Interview/Workshop	Interview questions SDQ – Parent version PSS STAR-P SRS EQ-5D	Interview questions SDQ – Parent version PSS
First Responders/Practitioners	Demographics Interview STAR-C	-	Reflective interview in last two months of pilot. STAR- C	Demographics Interview STAR-C	N/A

Table Two: Assessments for children and young people

Instrument used in the proposed trial	Number of items	Indicative completion time
Strengths and Difficulties Questionnaire Self-Report version for 11-17 year olds (Goodman et al., 1998)	25	10-15 minutes
Experiences of Services Questionnaire (Brown et al., 2014)	12 items, and 3 free text sections	8-10 minutes
KidCOPE (Spirito et al., 1998)	11 items	5-7 minutes
Child and Youth Resilience Measure (separate versions for 5-9 year olds, and 10-23 year olds) (McGarrigle & Ungar, 2019)	17	10-15 minutes
Session Rating Scale (Miller et al., 2000)	4	5-8 minutes
EQ-5D-Y (Wille., 2010)	5	5 minutes

Table Three: Instrument Summary and Rationale

Instrument used in the proposed trial	Evidence of suitability in different age/educational groups considered in the trial
Strengths and Difficulties Questionnaire (Goodman et al., 1998)	The SDQ is a brief behavioural and emotional screening questionnaire, routinely employed across youth mental health services to collect baseline data, usually at the point of referral. The SDQ captures information about children aged 2—17-year-olds. There is a version for young people aged 11-17years-old that they can complete on their own, and a parent version and teacher version. Only the parent version and young people's version will be used in the JRC study. Research with children and young people supports the use of the selfreport SDQ with young people aged 8-17-years-old and is therefore appropriate to our study.

	
Experiences of Services Questionnaire (Brown et al., 2014)	The ESQ is a brief questionnaire routinely employed across services to collect data relating to service satisfaction within Child and Adolescent Mental Health Services. The ESQ
	captures information about children aged 9-18-years-old. There is a version for children aged 9-11-years-old, a version for young people aged 12-18-years old, and a parent/carer version. All three version will be used within the JRC study.
KidCOPE (Spirito et al., 1998)	KidCOPE is a brief, clinical checklist designed to screen behavioural and cognitive coping in children and adolescents. The items focus on areas of coping such as problem solving, social support, social withdrawal, self-criticism, and emotional expression which are relevant to the current research. There are two age appropriate versions (7-12-years-old and 13-18years-old).
Short Mood and Feelings Questionnaire (sMFQ)	The Short Mood and Feelings Questionnaire (SMFQ) is a brief, self-report tool designed to assess depressive symptoms in children and adolescents. It consists of 13 items that evaluate mood-related symptoms, such as sadness, irritability, and low energy, over the past two weeks. Respondents rate the severity of each symptom on a 3-point scale, ranging from "not true" to "true." The SMFQ is commonly used in both clinical and research settings to help identify individuals who may be experiencing depression. It is a condensed version of the longer Mood and Feelings Questionnaire, offering a quicker and more accessible screening option.
Child and Youth Resilience Measure-revised (separate versions for 5-9 year olds, and 10-23 year olds) (McGarrigle & Ungar, 2019)	The CYRM-R is a screening tool used to explore the resources (individual, relational, communal, and cultural) available to young people which can aid their resilience. Therefore, the CYRM-R sees highly appropriate for the age group of the JRC study and due to the focus on resilience following crisis care.
Session Rating Scale (Miller et al., 2000)	The SRS is a simple, four-item visual scale used to assess dimensions of effective therapeutic relationships. The SRS has been used with children 6-12-years-old, and young people 13 years-old to adults.
EQ-5D-Y (Wille et al., 2010)	The EQ-5D-Y facilitates the description and measurement of child and adolescent health status, which combined with preference weights can be used to calculate utility to inform economic evaluations. It is widely used in HE evaluations (Hastings et al., 2020).

Assessments for parents/carers (estimated completion time = 55 minutes)

- 1. SDQ-parent version (Mathai et al., 2002) 10-15 minutes
- 2. Parental Stress Scale (Berry et al., 1995) 8-10 minutes
- 3. Session Rating Scale (Miller et al., 2000) 5-8 minutes
- 4. Experience of Services Questionnaire (Brown et al., 2014) 8-10 minutes
- 5. STAR-P, therapeutic experience scale with parents/carers (McGuire-Snieckus et al., 2007) 5 minutes
- 6. EQ-5D, records the patient's self-rated health on a vertical visual analogue scale where the endpoints are labelled for health economic data collection.

Throughout, participants will have no obligation to answer all questions / measures captured in the baseline assessments and will not be obliged to state their reasons for skipping certain items of measure.

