- 4. Time off work/school. NHS costs will be obtained from questionnaires to caregivers and young people at T1 and T2.
- 5. Time spent attending to emergencies compared to indirect work (note keeping, updating records), systemic liaison (e.g., safeguarding), and other duties, compared with idle time.
- 6. The cost implications of journey times in boroughs that are more rural and/or that present additional obstacles for the vehicle (e.g., busy one-way systems in intensely urban areas, rural roads with poor road surface conditions, the impact of climate at specific time points, etc.).

A micro costing approach will enable the analysis of detailed data on resource utilisation from NHS digital and unit cost data (available from: https://www.pssru.ac.uk/project-pages/unit-costs/) to generate precise estimates of economic costs. By clearly outlining all the costs occurred, other trusts can identify potential differences in costs related to roll-out. We will include the location of callouts, time to drive to and from each location, and qualitatively explore the perceived impact of location upon the service from the perspective of the attending first responders as a core part of workstream 3.

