6.6 Health Economic Data Analysis

We will perform a cost-consequence analysis of the MHJRC Service as a whole, as well as considering distributional impacts if data allows by age group, gender, sexual orientation, and ethnicity. We will provide, where appropriate, monetarised valuation of the effects of the programme and detail of who experiences them (younger person, young person's family, health service, police services). Heath and care utilisation can also be assigned a monetary value by applying NHS Reference Costs and the PSSRU unit costs. Health and wellbeing outcomes can be monetarised if appropriate. These can include calculating healthy life expectancies and disability free life years (NICE, 2013a; Shah et al., 2012).

Consequences will focus on the health and well-being impacts of the programme as well as impacts on the health service, including wait times for CAMHS services, attendance at A&E for mental health emergencies, police service call outs, to give a few examples, but this list is not exhaustive. Data for the benefits will come from the quantitative surveys in workstream two. We will supplement this data with data on health outcomes such as A&E attendance and waiting times from NHS digital and

data on contacts with the police using police data. We will compare these to the costs of implementing the programme, which will be obtained from The Greater Manchester Health & Social Care Partnership (GMHSCP) and PCFT. This will include considering costs around waiting times between call outs (e.g., costs for staff involved during the whole shift). Costs and consequences will be compared to the baseline scenario of service provision before the introduction of the MHJRC.

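### Table One gives two different visits the label T2 and schedules no EQ-5D-Y for young people at 6 months, so the cost-consequence analysis has no 6-month change on that measure

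*Protocol*

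**What the plan says.** Section 6.4 Data Collection sets the quantitative surveys at T1 (within 12 weeks of contact) and at a 6-month T2. Section 6.1 (Pathways 3 and 5) and the consent section also place T2 at 6 months, and the project summary caps follow-up at 6 months.

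Table One in 6.4.1 adds a column headed "In person/ video call T2 (3-month follow-up") beside a second in-person T2 column for 6 months. In the young people's row:

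- 3-month in-person cell: "ESQ KidCOPE CYRM-R EQ-5D-Y-3L Interview"
- 6-month in-person cell: "ESQ KidCOPE CYRM-R sMFQ Interview/Workshop"
- Qualtrics T1 cell, closing run: "SDQ – CYP ESQ SRS sMFQ CYRM-R KidCOPE Interview questions EQ-5D-Y"
- Qualtrics T2 cell: "Personal context Nature of crisis Demographics SDQ – CYP SMFQ CYRM-R KidCOPE Interview questions"

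Table Three says that the EQ-5D-Y, "combined with preference weights can be used to calculate utility to inform economic evaluations". Section 6.6 says: "Data for the benefits will come from the quantitative surveys in workstream two".

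**The concern.** The EQ-5D-Y is in the battery for the economic evaluation, and that evaluation takes its benefits from surveys run at T1 and 6 months. The schedule measures it at the start and then drops it at the only follow-up that the text recognises. Its one repeat sits in a column that no other section mentions and that carries the same label as the 6-month visit. Site staff cannot tell from the protocol whether a 3-month visit exists. If it does not, a change in EQ-5D-Y cannot be calculated for any young person. If it does, the change is available to 3 months, in person only.

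**Working it through.** No sample size, power or error rate is involved, so the check is a cell-by-cell reading of Table One against the text. The young people's row has five time-point columns and five cells, and they line up, so this does not look like a PDF-reading fault.

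| Table One column | EQ-5D-Y, young people | EQ-5D, parents/carers |
|---|---|---|
| In person, T1 | yes | yes |
| In person, T2 (3-month) | yes (as EQ-5D-Y-3L) | yes |
| In person, T2 (6-month) | no | yes |
| Qualtrics, T1 | yes | yes |
| Qualtrics, T2 | no | no |

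The Qualtrics T2 header gives no month; Pathway 5 in section 6.1 fixes it at 6 months.

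**Is the 3-month visit supported elsewhere?** No. Every section that dates T2 gives 6 months, and none outside the table mentions a 3-month contact.

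**Does the text supply the missing measure?** No. The 6.4.1 list for T2 repeats ESQ, KidCOPE, CYRM-R and PSS only. That list does not match the table in other respects: it leaves out the sMFQ, STAR-P and parent EQ-5D that Table One has at 6 months in person. In the other direction, 6.4.1 places the SDQ at T1 and T2, but the young people's 6-month in-person cell lacks it. Table and text have not been reconciled.

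**Count of EQ-5D-Y assessments per young person, as written:**

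- In person: T1 = 1, 3 months = 1, 6 months = 0.
- Online: T1 = 1, T2 = 0.

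The planned number is 100 + 100 = 200 young people at most. The number due a T2 may be smaller, because the two-year retrospective Qualtrics route has no T2 by design. The count with EQ-5D-Y at 6 months is 0 whichever denominator is used.

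**Can imputation fill the gap?** Section 6.6 says missing data will be imputed. With no young person observed on EQ-5D-Y at 6 months, the study would hold no data from which to estimate the imputation model.

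**The case against.** The strongest reply is that little depends on this instrument. The analysis is cost-consequence, with no committed QALY or utility endpoint. Section 6.6 values health outcomes in money only where suitable and avoids a summary judgement of effectiveness. Neither 6.4.3 nor 6.6 names the EQ-5D-Y. Other 6-month outcomes remain: sMFQ, CYRM-R and KidCOPE in both modes, with ESQ in person and SDQ online. Service and police data come from records. This stands, and it limits the size of the point to one consequence.

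The omission may also be deliberate. The 6.4.1 list agrees with the table on it, the questionnaire list other than the SDQ is provisional, and the online route is meant to spare families. That is possible, but the protocol does not say so, and the 6.4.1 list is too incomplete at T2 to show intent. Table One is also the schedule to which the recruitment pathways send the reader.

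Three stronger readings are tempting, and the document does not support them:

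- *Service use and time off school have no scheduled collection.* Section 6.4.3 adds days-missed questions to the data collection points and says: "NHS costs will be obtained from questionnaires to caregivers and young people at T1 and T2". At most, Table One should name the form.
- *Parents' utility is followed while young people's is not.* The parent assessment list describes the EQ-5D only by its visual analogue scale, so the protocol does not establish that it yields a utility.
- *No young person has any EQ-5D-Y follow-up.* That requires ignoring a column that the table contains. It holds for online participants only, unless the 3-month visit turns out not to exist.

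**Conclusion.** The point holds in limited form. Table One uses T2 for two different visits, against a text that has only the 6-month one. On the schedule as written, no young person gives an EQ-5D-Y at 6 months, and online participants give no follow-up EQ-5D-Y at all. The cost-consequence analysis loses the change in young people's generic health status or utility to 6 months and is not otherwise disabled. Whether in-person participants have a change to 3 months depends on whether that visit is real, which the protocol leaves open.

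This rests on two assumptions: that Table One is the operative schedule, and that the instruments in the provisional list are in use. It should be settled while follow-up is running. Section 7 has data collection finishing by 31 March 2026, and a missed T2 measurement cannot be obtained afterwards.

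**What to change.** Amend section 6.4.1 as follows:

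1. Add EQ-5D-Y to the young people's 6-month in-person cell, to their Qualtrics T2 cell and to the T2 list in the text.
2. Add EQ-5D to the parents' Qualtrics T2 cell.
3. Either delete the 3-month column, or give it its own label and carry it into section 6.4, so that T2 means 6 months throughout.

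If the sponsor does not intend to follow EQ-5D-Y to 6 months, the protocol should say so in 6.4.1 and 6.6, and the label still needs correcting. Naming the service-use and days-missed items in Table One at the same time would be helpful tidying.

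The cost is a protocol amendment and about 5 minutes per participant at T2. Table Two gives 5 items and 5 minutes for the EQ-5D-Y. The protocol gives no time for the parent EQ-5D, which is assumed to be similar. Young people whose T2 has already passed will stay without a 6-month value, and the report should give their number.
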